3.2 Endpoints

- *Safety*: To describe AEs in subjects receiving the combination of PIO and TKI. AEs will be graded according to the Common Terminology Criteria for Adverse Events (**CTCAE**) v.4.03 assessed through scheduled assessment and subject reported diary
- *Efficacy*: To determine the proportion of subjects who maintain MMR following a second discontinuation of TKI.

3.3 Description of Treatment

Trial will be discussed with subjects in the out-patient clinic. Interested subjects will be offered to participate in the study. The primary physician (co-investigator) will discuss the study and counsel both subject and family. The objectives of the study, procedures, alternative therapies and potential risks and benefits of participation will be explained. Subject will be given the time to read the consent and the opportunity to ask questions before signing the consent form approved by Institutional Review Board (**IRB**). Protocol registration procedures will be completed within 48 hours of enrollment. Eligibility checklist form will be completed prior to enrollment.

Eligible subjects will start PIO 30 mg/d orally for 2 cycles (56 days) and then increase to 45 mg/d. Subjects will either start or continue the same TKI at the pre-discontinuation doses. After initiation of PIO, blood qRT-PCR for *BCR-ABL1* will be collected on a monthly basis. Disease status will be monitored by blood qRT-PCR for *BCR-ABL1* at study specific time points (**Figure 7**).

4. Selection of Study Population

4.1 *Inclusion Criteria*

1. CML in any phase
2. Philadelphia chromosome positive acute lymphoblastic leukemia
3. Loss of MMR following a first TKI discontinuation trial
4. Age \geq 16 years
5. Serum bilirubin <1.5 x upper limit of normal values
6. AST (SGOT)/ALT (SGPT) <2.5x upper limit of normal values
7. Females of child bearing potential must agree to abstain from sexual activity or to use a medically approved contraceptive measure/regimen during and for 3 months after the treatment period. Women of child bearing potential must have a negative urine pregnancy test at the time of enrollment. Acceptable methods of birth control include oral contraceptive, intrauterine device, transdermal/implanted or injected contraceptives and abstinence.
8. Patient requiring anti-diabetic medications to manage hyperglycemia are eligible. Adjustments of other anti-diabetic agents will be made with close monitoring of blood glucose
9. Males must agree to abstain from sexual activity or agree to utilize a medically-approved contraception method during and for 3 months after the treatment period.
10. Informed consent
11. Be able and willing to comply with study visits and procedures

4.2 *Exclusion Criteria*

1. Known loss of CCyR by marrow cytogenetic or blood FISH for *BCR-ABL1*
2. Loss of CHR
3. Participation in another clinical trial with any investigative drug within 30 days prior to study enrolment
4. Chronic graft-versus-host disease requiring systemic immunosuppression post-allogeneic hematopoietic stem cell transplantation
5. Cardiovascular disease: history of congestive heart failure, myocardial infarction within the 6 months of study entry, symptomatic cardiac arrhythmia requiring treatment
6. History of bladder cancer
7. Gross (visible) hematuria
8. Known history of osteoporosis
9. Known history of macular edema
10. Known history of ABL1-domain mutation that predicts resistance to the discontinued TKI
11. Significant medical or psychiatric disorder that would interfere with consent, study participation, or follow-up
12. Known allergy to PIO
13. Pregnant or breastfeeding
14. Use of TZD within 28 days prior to enrollment

15. Significant gastrointestinal condition that could potentially impair the absorption or disposition of the drug
16. Uncontrolled peripheral edema (2+ or more) of any etiology.
17. Active cancer that requires therapy in the form of chemotherapy or radiation

5. Study Procedures

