12.1 Case Report Forms and Study Records

12.2 Source Documents

12.3 Retention of Data

12.4 Study Termination

13. References

14. Appendix 1 and 2

PROTOCOL SYNOPSIS

Study Treatments	Pioglitazone
Study Title	Combination of Pioglitazone and Tyrosine Kinase Inhibitor (TKI) in Relapsed Chronic Myeloid Leukemia Following a TKI Discontinuation
Phase	II
Summary and Study Rationale	Approximately 40-60% of patients with chronic myeloid leukemia (CML) who discontinue imatinib (IM) or second-generation TKI after sustained deep molecular remission will experience molecular relapse, but regain molecular response after restarting TKI. The success rate of a second TKI discontinuation trial is low (25%), and continuous TKI is recommended for these patients. Pioglitazone (PIO) is a well-tolerated orally bioavailable Peroxisome Proliferator-Activated Receptors, (PPARγ) agonist with in vitro BCR-ABL1 tyrosine kinase inhibition activity that is synergistic with TKI. In this study, we will assess safety and efficacy of PIO combined with TKI in CML patients with molecular relapse following a first TKI discontinuation trial. Success of a second TKI discontinuation trial, following 6 months of sustained deep molecular response while on PIO and TKI combination will be assessed.

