Study Design	This is a single-center, prospective, phase II trial. For the purposes of this protocol and all analyses, a cycle of treatment is defined as 28 days. Eligible subjects will start PIO in addition to TKI, at 30mg/d for 2 cycles (56 days) and, in the absence of grade 2 or higher toxicities, increase to 45mg/d. Subjects will receive PIO in addition to TKI for 6 months from the first documented \leq molecular response (MR) ^{4,5} and if subjects maintain \leq MR ^{4,5} for 6 months with less or equal than 2 BCR/ABL1 transcript fluctuation $<$ major molecular response (MMR) will be eligible for a second TKI discontinuation. Subjects who fail to achieve MMR after 4 months, or \leq MR ^{4,5} after 6 months of the combination treatment of PIO and TKI will be taken off treatment. Subjects who lose MMR while on the combination will be taken off study and managed at the discretion of the treating physician. While the combination of PIO and TKI, blood quantitative real time Polymerase Chain Reaction (qRT-PCR) for BCR-ABL1 will be collected on a monthly basis, and after discontinuation of PIO and TKI, disease be monitored by blood qRT-PCR for BCR-ABL1 obtained monthly for the first 3 months, quarterly for 1 year, and then bi-annually for 1 year.
Study Objectives	
 To assess safety of the combination of PIO and TKI in CML subjects who experience a loss of MMR following a first TKI discontinuation To assess survival without loss of MMR following a second TKI discontinuation trial in subjects who achieve or maintain \leqMR^{4,5} for at least 6 months with the combination PIO and TKI
Study Endpoints	
 Safety: To describe adverse events (AE) in subjects receiving the combination of PIO and TKI. AEs will be graded according to the Common Terminology Criteria for Adverse Events (CTCAE) v.4.03 assessed through scheduled assessment and subject reported diary To determine the proportion of subjects who maintain MMR following discontinuation of PIO and TKI using blood qRT-PCR for BCR-ABL1 obtained monthly for the first 3 months, quarterly following 1 year and bi-annually thereafter.
Diagnosis and Main Inclusion Criteria	Age \geq 16 diagnosed with CML in any phase Molecular relapse (loss of MMR) post-first TKI discontinuation trial Complete cytogenetic and complete hematologic response

Number of Subjects	26 subjects
Duration of Subject Participation	2 years

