1.2 Definitions of Response in CML

Several organizations, such as the European Leukemia Net (**ELN**) and the National Comprehensive Cancer Network (**NCCN**), provide extensive evidence based recommendations that define response and provide milestones or algorithms to monitor response on TKIs (<http://www.nccn.org/clinical.asp>) [3]. Response criteria for hematologic, cytogenetic (based on metaphase cytogenetic preparations), and molecular responses (**MR**) are shown in **Table 1**. In the absence of universal standards or reagents, the International Scale (**IS**) was developed to harmonize MRs across laboratories by applying a laboratory specific conversion factor [4]. All molecular response criteria and recommendations for intervention in the NCCN or ELN guidelines are based on IS molecular responses. Major molecular response (**MMR**) is defined by a level of *BCR-ABL1* transcript by quantitative Real-Time Polymerase Chain Reaction (**qRT-PCR**) of

Table 1. Definitions of Response in CML

Response	Definition
Hematologic	
Complete (CHR)	WBC $< 10 \times 10^9/L$ Basophils $< 5\%$ No myelocytes, promyelocytes, myeloblasts in the differential Platelet count $< 450 \times 10^9/L$ Spleen nonpalpable
Cytogenetic[*]	
Complete (CCyR)	No Ph+ metaphases
Partial (PCyR)	1% to 35% Ph+ metaphases
Minor (mCyR)	36% to 65% Ph+ metaphases
Minima (minCyR)	66% to 95% Ph+ metaphases
None (noCyR)	$> 95\%$ Ph+ metaphases
Molecular[†]	
Major (MMR)	Ratio of BCR-ABL1 to ABL (or other housekeeping genes) $\leq 0.1\%$ on the IS
MR ^{4.0}	Ratio of BCR-ABL1 to ABL $< 0.01\%$
MR ^{4.5}	Ratio of BCR-ABL1 to ABL $< 0.032\%$
MR ^{5.0}	Ratio of BCR-ABL1 to ABL $< 0.001\%$

<0.1%, MR⁴ by a *BCR-ABL1*< 0.01%, MR⁴ by a *BCR-ABL1*< 0.0032%, and MR^{5.0} by a *BCR-ABL1*< 0.001%. Complete molecular remission (CMR) is defined by a *BCR-ABL1* level < MR^{4.5}.

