1.3 Tyrosine Kinase Inhibitor Discontinuation Trials

Although TKIs dramatically improved CML patient outcomes and improved quality of life compared to previous treatments, therapy with a TKI is currently life-long therapy, requiring patients to take medication daily and to make frequent visits for monitoring. Patients often exposed to chronic, frequently low grade adverse events (AE), and negative emotional consequences can manifest even in the absence of overt disease symptoms [5]. Thus, daily adherence to TKI therapy might be challenging for a significant proportion of patients. However, TKI may not appear to be needed as a lifelong therapy. Recent data suggests that in patients in CP and AP treated with IM for ≥ 3 years and who have maintained CMR for at least 2 years, IM can be safely discontinued without reappearance of the *BCR-ABL1* in approximately 40~60% of patients, and these remissions are durable. (Figure 1. A~D) [6-9]. Although *BCR-ABL1* becomes detectable in the other 40~60% within a year from IM discontinuation, reinstitution of IM is associated with a second molecular remission in all cases. No patients transformed to BC on any of these discontinuation trials. Similar to IM, discontinuation of the second-generation (2G) DAS or NIL used in front-line or for IM intolerance or resistance is associated with a 60% treatment-free survival without loss of MMR [10].

However, for CP-CML patients who lose MMR after first IM discontinuation and regain CMR following a restart of IM, the current recommendations are to keep these patients on IM lifelong given the low success rates (25%) of a second TKI discontinuation trial [11].

[figure not shown]

Figure 1. Molecular relapse free survival following imatinib discontinuation: A. data on 100 patients; B. data on 40 patients, C. data on 43 patients; D. data on 48 patients

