1.6 Rationale for the Study

New approaches are needed for the management of the 50% of CML patients who experience a molecular relapse following a first trial of TKI discontinuation. Given the potential risks of long-term TKI exposure, the contra-indication for pregnancies/child conception while on TKI, and the expenses associated with the use of these agents (92,000 USD/year for IM, > 120,000 USD/year for DAS or NIL), many patients express interests in TKI discontinuation trials. However, with the low success rate of a second discontinuation trial (20%), patients who fail their first TKI discontinuation have currently no other option but to continue TKI therapy.

Given the interactions between PPAR γ and STAT5 in CML LSCs, the synergy between PIO and IM [41], and the safety profile of PIO, a trial testing the combination of PIO and TKIs is a reasonable novel approach to eradicate minimal residual disease in CML .

2. Study Objectives and Hypothesis

2.1 *Objectives*

- To assess safety of the combination of PIO and TKI in CML subjects who experience a loss of MMR following a first TKI discontinuation
- To assess survival without loss of MMR following a second TKI discontinuation in subjects who achieve or maintain \leq MR^{4,5} with the combination PIO and TKI administered for at least 6 months

2.2 *Hypothesis*

Subjects who lose MMR after a first TKI discontinuation trial, but are still in CCyR and CHR regardless of their molecular status, will be offered enrollment on this trial. We hypothesize that PIO in combination with TKI will be well tolerated and that subjects will achieve or maintain \leq MR^{4,5} with the combination of TKI and PIO. Subjects who achieve \leq MR^{4,5} will be offered a second TKI discontinuation trial. We also hypothesize that MMR will be sustained following a second TKI discontinuation in at least 50% of subjects.

3. Investigational Plan

3.1 *Overall Study Design and Plan*

This is an open-label phase 2 study in which eligible subjects will receive PIO in combination with TKI. Safety of PIO in combination with TKI will be assessed continuously. Subjects who lose MMR while on the combination will be taken off study and managed at the discretion of the treating physician. Loss of MMR is defined by a detectable *BCR-ABL1* level $>0.1\%$ and confirmed within 4 weeks. For the purposes of this protocol and all analyses, a cycle of treatment is defined as 28 days. Study schema is depicted in Figure 7.

[figure not shown]

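### Section 4.1 admits Ph+ ALL, and section 9.4 would count those subjects in a go/no-go whose 20% null has no stated basis for that disease

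*Combined protocol and SAP*

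**What the plan says.** Section 4.1 numbers its inclusion criteria. Item 1 is CML in any phase and item 2 is "Philadelphia chromosome positive acute lymphoblastic leukemia". No 'or' joins them.

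These parts of the protocol name CML only:
- The title: "Combination of Pioglitazone and Tyrosine Kinase Inhibitor (TKI) in Relapsed Chronic Myeloid Leukemia Following a TKI Discontinuation".
- The synopsis inclusion criterion: "diagnosed with CML in any phase". Ph+ ALL is not listed there.
- The first objective (section 2.1): "To assess safety of the combination of PIO and TKI in CML subjects who experience a loss of MMR following a first TKI discontinuation".
- The response criteria (section 1.2): "Table 1. Definitions of Response in CML".
- The disease history taken at screening (section 5.1, Table 3 and its note 3), which asks for CML history and the date of CML onset.

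Two success rates are given for a second discontinuation. Section 1.3 speaks "for CP-CML patients who lose MMR after first IM discontinuation and regain CMR following a restart of IM" and advises lifelong treatment "given the low success rates (25%) of a second TKI discontinuation trial". Section 1.6 gives 20% in a paragraph about CML patients. Neither section gives a rate for Ph+ ALL.

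Section 9.4 sets a 20% null and a 50% alternative, with 9 evaluable subjects in Stage 1 and 24 in all. It does not restrict evaluable subjects by diagnosis. Section 9.5 lists underlying diagnosis among the subgroup factors for the efficacy endpoints.

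**The concern.** The eligibility list admits a disease that the rest of the design does not provide for. Section 9.4 has no counting rule by diagnosis, so any Ph+ ALL subject who reaches evaluability is one of the 9 or the 24 and is judged against a null that the documents support, if at all, only for CML.

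The decision turns on 9 successes among 24, so a few subjects with a different success rate can move both error rates. The conclusion would also describe a mixed population, while the first objective is about CML subjects. The ambiguity reaches the analysis sets too: section 9.2 removes subjects who fail an eligibility criterion from the per-protocol population, and eligibility by diagnosis is the unclear item.

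**Working it through.** **Inputs from section 9.4.** Null 20%, alternative 50%. Stop if 2 or fewer of 9 succeed; the result is positive if at least 9 of 24 succeed.

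**The plan's own figures.** An exact search with the stated 20%, 50%, 5% alpha and 80% power gives an optimal design of 8 then 18 in total, not 9 then 24. That is a separate matter. The rule is taken here as written.

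**All-CML baseline.** With X1 ~ Bin(9, p) and X2 ~ Bin(15, p),

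P(go) = sum over x = 3 to 9 of P(X1 = x) × P(X2 ≥ 9 − x).

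- p = 0.5: 0.1641×0.8491 + 0.2461×0.9408 + 0.2461×0.9824 + 0.1641×0.9963 + 0.0703×0.9995 + 0.0176 + 0.0020 = 0.866 (power).
- p = 0.2: 0.17616×0.06105 + 0.06606×0.16423 + 0.01652×0.35184 + 0.00275×0.60198 + smaller terms = 0.029 (alpha).

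**With k Ph+ ALL subjects among the 24, in random order.** The number j that falls in Stage 1 has probability C(k, j)·C(24−k, 9−j)/C(24, 9). Given j, X1 is the sum of Bin(9−j, CML rate) and Bin(j, ALL rate). X2 is the sum of Bin(15−k+j, CML rate) and Bin(k−j, ALL rate). P(go) is averaged over j.

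Example, k = 1, CML 50%, Ph+ ALL 0%: (9/24)×0.8020 + (15/24)×0.8451 = 0.829. With Ph+ ALL at 20%: 0.375×0.8275 + 0.625×0.8534 = 0.844.

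**Results under the section 9.4 rule.** The number of Ph+ ALL subjects and their success rates are assumptions.

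| Ph+ ALL among 24 | Power: CML 50%, Ph+ ALL 0% to 20% | Alpha: CML 20%, Ph+ ALL 40% to 60% |
|---|---|---|
| 0 | 86.6% | 2.9% |
| 1 | 82.9% to 84.4% | 3.7% to 4.4% |
| 2 | 78.4% to 81.9% | 4.5% to 6.4% |
| 4 | 66.6% to 75.9% | 6.7% to 12.4% |

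**Dependence on the Stage 1 rule.** The synopsis and section 12.4 stop at fewer than 2 of 9, not at 2 or fewer. The same sums started at x = 2 give:

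| Ph+ ALL among 24 | Power, same assumptions | Alpha, same assumptions |
|---|---|---|
| 0 | 91.5% | 3.5% |
| 1 | 88% to 90% | 4.3% to 5.2% |
| 2 | 84% to 87% | 5.3% to 7.5% |
| 4 | 73% to 82% | 7.9% to 14.6% |

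The direction is the same under either rule.

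**The case against.** **Section 9.5 may show intent.** A subgroup by underlying diagnosis fits a plan that expected more than one disease, and it would yield some separate reporting. A reader might infer that the protocol is about CML everywhere outside item 2; this factor is a reason not to say so, although it could also mean CML phase. It still supplies no null rate or counting rule, and a subgroup table does not take anyone out of the Simon count.

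**The list may just lack an 'or'.** A reader might infer that items 1 and 2 must both hold, so that nobody qualifies, especially as section 5.2.2 has staff confirm every inclusion criterion. The list does not support that reading: items 7 and 9 apply to one sex each and item 8 is permissive. Two admissible diagnoses is the sensible reading, and it is the one used here.

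**The endpoint can be measured.** MMR and MR4.5 are BCR-ABL1 transcript ratios, and item 3 requires prior loss of MMR. This stands. Table 1's title does not make the ratio undefined in Ph+ ALL. The gap lies in the benchmark and the counting, not in the assay.

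**The population is already mixed.** Item 1 admits CML in any phase, while the 25% is for chronic phase. This also stands, and restricting the counts to CML would not remove that heterogeneity.

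**The effect may be small.** The documents give no expected number of Ph+ ALL subjects, and the institutional series in section 1.3 is 24 subjects, all with CML. This limits the size but does not settle how such a subject is counted.

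**Conclusion.** The inconsistency is real and should be resolved. Section 4.1 admits Ph+ ALL, section 9.4 counts such subjects, and nothing in the documents justifies a 20% null for them.

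The size is conditional. Under the section 9.4 rule one Ph+ ALL subject leaves both error rates within plan over the ranges tried (power at least 82.9%, alpha at most 4.4%). With two, power can fall just below 80% or alpha rise just above 5%. With four, the planned 80% power is missed throughout the lower range, or the planned 5% alpha is exceeded throughout the upper range.

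A reader might take the four-subject row as the expected impact. The documents do not support that: they give no Ph+ ALL share, success rate or relapse risk. The two columns also rest on opposite assumptions about Ph+ ALL, so they are alternatives and not joint harms. A single rate between 20% and 50% would move both error rates the wrong way, but more mildly. If Ph+ ALL subjects had the same success rate as CML subjects, neither figure would change.

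A reader might also infer that the 20% null was drawn from chronic-phase CML. Only the 25% in section 1.3 is tied to chronic phase. The 20% in section 1.6 concerns CML patients generally, and section 9.4 cites no source. That the null is a CML rate is an inference from these being the only second-discontinuation rates given.

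**What to change.** Reconcile section 4.1 with the title, synopsis and objectives, in one of two ways:

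1. Remove item 2, so that the trial enrolls CML only.
2. Join items 1 and 2 with 'or', and state in section 9.4 that the Stage 1 and final Simon counts use CML subjects only. Keep Ph+ ALL subjects in the safety population and describe their efficacy results separately.

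Make the choice before the Stage 1 results are known, since deciding afterwards who counts would be post hoc.

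The first option is a wording amendment; its cost is that Ph+ ALL patients cannot enter. The second costs more than a sentence in section 9.4. Ph+ ALL subjects would not count toward the 24, and the total of 26 leaves only 26 − 24 = 2 places, both meant for dropout. Each Ph+ ALL subject therefore uses one of the 26 places or must be enrolled in addition. The synopsis, the objectives and the analysis-population text in section 9.2 would need matching edits.

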5.1 Schedule of Events

The following describes the procedures/tests required for this study:

Screening, on study, and end of study procedures are shown in **Table 3**. Screening tests and procedures to establish eligibility of the subject for the trial will be done within 14 days prior to initiation of study drug. Evaluation, visit samples or activities should occur within range defined below.

Table 3. Schedule of Events

	Screening ± 14days	Day1	On PIO and TKI		Off PIO and TKI		End of Treatment	12 Long-Term Follow up
			Evaluations on day 14 ± 2days	Evaluations on days 28 ± 2days then monthly ± 2days	Monthly Evaluations ± 2days for first 3 months	Quarterly Evaluations ± 7days for one year		
¹ Informed Consent and Registration	X							
² History and Demographics	X							
³ CML history, prior therapy, and response	X							
⁴ Vital Signs, Physical Examination	X		X	X			X	
⁵ Concomitant medications	X		X	X			X	
⁶ CBC and differential, and Serum Chemistries	X		X	X			X	
⁷ Urine HCG	X							
⁸ Blood qRT-PCR for BCR-ABL1	X			X	X	X	X	X
⁹ Diary card			X	X				
¹⁰ MMAS-8			X	X				
¹¹ Adverse Events Assessments		X						→
PIO administration		X		X				

¹**Informed Consent:** All subjects must take part in the informed consent process prior to any study related activity. During the consent process, the person obtaining consent must inform the subject of all elements of informed consent. Adequate time must be allowed for questions and for the subject to make a voluntary decision. No protocol-specific procedures are to be performed until the subject has signed and dated the

IRB approved informed consent form. Each subject's participation in the trial begins with the signing and dating of the informed consent form.

²*Medical/Surgical History and Demographics:* Medical/surgical history that includes diagnoses and therapies as well as demographic information that consists of the subject's age, gender, race, and ethnicity will be recorded.

³*CML History, Prior Therapy, and Response:* The initial presentation history and pathology including the date of onset of CML must be recorded. TKI therapy including date of initiation and stop, doses, dose reductions or interruptions will be recorded. Sequential monitoring response to therapy and date of first TKI discontinuation, as well as post-discontinuation monitoring data will be collected. If TKI was restarted prior to enrollment on study, date of re-initiation, and dosing information, as well as response monitoring data will be collected.

⁴*Vital signs and Physical Examination:* Vital signs including temperature, pulse, and blood pressure, and complete physical examination, including weight, must be performed at screening, day 14 and 28 as part of study. After that, this will be done every two to three months as part of standard of care unless new symptoms occur.

⁵*Concomitant medications:* All prescribed, over the counter, and supplemental/herbal medications, including route of administration (oral, topical, intravenous, rectal, subcutaneous, etc.), frequency, and duration will be recorded.

⁶*Complete Blood Count (CBC), differential and Serum Chemistries:* CBC with automated differential and serum chemistries will be obtained at screening as part of standard of care, and day 14 and 28 as part of study. After that, this will be done every two to three months as part of standard of care unless new symptoms occur.

⁷*Urine human chorionic gonadotropin (HCG):* HCG will only be performed in pre-menopausal women of childbearing age with no history of hysterectomy or bilateral tubal ligation.

⁸*Blood qRT-PCR for BCR-ABL1:* Blood qRT-PCR for *BCR-ABL1* will be obtained monthly while on PIO and TKI. Following discontinuation of TKI, monthly blood qRT-PCR for *BCR-ABL1* for the first 3 months, quarterly for a year and bi-annually thereafter will be done as part of standard of care.

⁹*Diary card:* A diary card will be completed daily to indicate the date and approximate time of administration of each dose of PIO and TKI, including any deviations from schedule such as missed or repeated doses. (**Appendix 1**)

¹⁰*Morisky Medication Adherence Scales – 8 (MMAS-8):* A MMAS-8 will be completed at each clinic visits while on PIO and TKI. (**Appendix 2**)

¹¹*Adverse event assessments:* All AEs will be assessed at each clinic visit as part of standard of care regardless the event is considered related to the treatment or not.

End of Treatment or Early Termination Procedures: The End-of-Treatment (or early termination) Visit should be performed within 2 weeks (14 days) of the subject's last dose of study drug or the subject/investigator decision to end treatment, whichever is later. Subjects will also return to the clinic or

will be contacted for a safety follow-up assessment 30 days \pm 3 days after the last dose of study drug was taken.

¹²*Long Term Follow-up:*

- **Safety:** All AEs ongoing or starting within 30 days after the End-of-Treatment must be recorded on the case report form (CRF). After this time, ongoing AEs thought to be at least possibly study-drug related and all ongoing serious adverse events (SAE) should be followed at least every 4 weeks until they resolve to baseline (or CTCAE grade ≤ 1), stabilize, or are considered to be chronic or irreversible.
- **Relapse-free Survival:** After 2 years of follow-up off TKI, if MMR is lost at any time, or if subjects withdraw from study for toxicity or any reasons, information on disease status (qRT-PCRs) will be collected once a year for 5 years as part of the Long-Term Follow-up. This information does not need to be obtained during a visit; review of local hematologist's records is acceptable.

5.2 **Description of Study Visits**

5.2.1 **Visit 1 (Day -14 to -1): Screening**

- Obtain written informed consent
- Record demographic data including age, gender, and race
- Review medical, surgical, and CML history described above.
- Record prior and concomitant medications including start/stop dates, indication, dose and frequency taken within 30 days of Day 1.
- Collect blood samples for CBC with differential count and serum chemistries.
-
- Collect urine for pregnancy test for female subjects who are not postmenopausal or surgically sterile. If positive, repeat and confirm results within a week and prior to start of study drug. A second positive test will result in exclusion of the subject from the study.
- Unless done within 72 hours, measure and record height in cm and weight in kg, record vital signs. Measure body temperature, systolic / diastolic blood pressure (BP) and pulse rate. Perform and record physical examination.
- Collect blood samples for qRT-PCR of *BCR/ABL1* unless done it within 30 days

5.2.2 **Visit 2 (Day 1): Baseline/Drug Dispensing/Initiation of Treatment**

- Review and document all inclusion and exclusion criteria to ensure that subjects meet all inclusion criteria and none of the exclusion criteria.
- Record AEs as part of standard of care.
- Dispense PIO at 30 mg/d and instruct subjects how to take study drug, daily every 24 hours and how to fill the diary card.

5.2.3 **Visits 3 (Days 14 \pm 2): Early Follow-up**

- Measure and record height in cm and weight in kg. Record vital signs. Measure body temperature, systolic/diastolic BP and pulse rate. Perform and record physical examination.

- Record medications including start/stop dates, indication, dose and frequency for any changes since previous visit.
- Collect blood samples for CBC with differential count and serum chemistries.
- Assess study drug compliance by pill count, review of the diary card and MMAS-8.
- Assess and record AEs and SAEs

5.2.4 Visits 4+ (Day 28 ±2, then q28+/-2 days during combination of PIO and TKI)

- On day 28, measure and record height in cm and weight in kg. Record vital signs. Measure body temperature, systolic / diastolic BP and pulse rate. Perform and record physical examination. Unless new symptoms occur, these will be performed every other month as part of standard of care.
- On day 28, record medications including start/stop dates, indication, dose and frequency for any changes since previous visit. Unless new symptoms occur, these will be performed every other month as part of standard of care.
- On day 28, collect blood samples for CBC with differential count and serum chemistries. Unless new symptoms occur, these will be performed every other month as part of standard of care.
- On day 56, in the absence of grade 2 or higher toxicities, PIO doses will be increased to 45 mg/d
- Dispense drug supply for self-dosing, remind subjects of dosing instructions, and obtain all unused study drug
- Assess study drug compliance by pill count, review of the diary card and MMAS-8.
- Collect blood samples for qRT-PCR of *BCR/ABL1* every month.
- Assess and record AEs and SAEs continuously

5.2.5 Post-discontinuation of PIO and TKI Visits (Monthly for 3 months ± 2 days and quarterly ±7 days for 1 year and biannually thereafter)

- Collect blood samples for qRT-PCR of *BCR/ABL1* as part of standard of care
- Assess and record AEs and SAEs continuously

